5.8.2. Laboratory Data

5.8.2.1. Haematology, Coagulation, Biochemistry tests

Biological parameters will be described at inclusion, D1, D5, D9, D13, D18 and D23 of each course of chemotherapy. The concerned biological parameters are the followings:

- Haematology
 - Haemoglobin (g/dL)
 - Hematocrit (%)
 - Erythrocytes (T/L)
 - Leukocytes (G/L)
 - Neutrophils (G/L)
 - Blasts (%)
 - Platelets (G/L)
- Blood coagulation
 - Activated Partial Thromboplastin Time (aPTT) (sec)
 - Prothrombin time (%)
 - Fibrinogen (g/L)
 - Antithrombin III (%)
 - INR
- Blood biochemistry
 - Albumin (g/L)
 - Plasma Bicarbonate (mmol/L)
 - Creatinine clearance (mL/min)
 - Serum Creatinine
 - Glycaemia (mmol/L)
 - Alkaline Phosphatase (U/L)
 - AST (U/L)
 - ALT (U/L)
 - Cholesterol (mmol/L)
 - LDH (U/L)
 - Gamma-GT (U/L)
 - Bilirubin (μmol/L)
 - Triglycerides (g/L)
 - Sodium (mmol/L)
 - Potassium (mmol/L)
 - Calcium (mmol/L)
- Pancreas
 - Lipase (U/L)
 - Amylase (U/L)

Raw results as well as absolute and relative change from baseline will be described at each timepoint between treatment groups.

Absolute change in the biological parameter between visit V_i and baseline will be calculated according to the formula: $\text{biological parameter at } V_i - \text{biological parameter at baseline}$

Relative change in biological parameter between visit V_i and baseline will be calculated according to the formula: $\frac{\text{biological parameter at } V_i - \text{biological parameter at baseline}}{\text{biological parameter at baseline}} \times 100$

All laboratory data will be provided in data listings. A subset listing will be presented for all clinically significant abnormal laboratory values. Data will be summarized by treatment group and patients with laboratory values of NCI-CTCAE grade 3 or 4 will be identified.

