8.5.4 Dosage modifications for GRASPA

- If patient cannot receive GRASPA, for another reason than an adverse event, treatment may be postponed no later than one week after the initial scheduled day. A minimum two weeks interval between GRASPA infusions must be insured.
- In case of allergic reaction during administration, stop the administration immediately and then to administer the necessary symptomatic treatments, according to standard of care. Further administration of GRASPA will be at investigator judgment, considering possibility of premedication anticipated for such case.
- In case of any Grade 3 or 4 adverse event related to GRASPA occurring in two successive infusions, GRASPA should be discontinued.
- In the event of bilirubin levels >3 times upper limit of normal or transaminase levels >10 times upper limit of normal, treatment with GRASPA should be discontinued.

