8.7 Laboratory assessments

8.7.1 Biological parameters

Biological assessment will be performed according to the investigational center procedure at inclusion, and then, at D1, D5, D9, D13, D18, D23 and D27 of each course of chemotherapy (± 2 days).

Following measurement should be performed:

- Hematology: Complete Blood Count (CBC), platelets;
- Coagulation parameters: Prothrombin Time (PT), activated Partial Thromboplastin Time (aPTT), fibrinogen, antithrombin III, INR;
- Chemistry: bicarbonate, sodium, potassium, calcium, creatinine, creatinine clearance (calculated by Cockroft & Gault formula), albumin, bilirubin, alanine amino transferase (ALT), aspartate amino transferase (AST), alkaline phosphatase, gamma glutamyl transpeptidase (GGT), lactate dehydrogenase, glucose, cholesterol, triglyceride, lipase, amylase;
- Serologic test for HIV, B and C hepatitis will be made at inclusion only, if needed.
- Serum pregnancy test for women with childbearing potential at inclusion and end of treatment.

Assessed and signed anonymized lab reports must be sent to sponsor/representatives as soon as possible after receiving the results for protocol required tests as well as for any testing performed for management of AEs.

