8.10 Study visits assessments and procedures

• Inclusion Visit (within max 4 weeks before treatment initiation):

During the inclusion visit, the following procedures/assessments will be performed:

- Patient information about potential study participation and obtaining the signed informed consent before any study related procedures;
- Patient demographics: date of birth, gender;
- ECOG performance status
- AML characteristics and assessment (see section 8.6): qualitative and quantitative parameters, primary diagnostic date, baseline values for bone marrow blast count, cytogenetic analysis, FAB and WHO classifications, including extramedullary AML assessment
- Medical history (relevant for the study condition) and concomitant medications
- General physical examination by systems and organs, including routine ECG, weight and height measurements
- Biological assessment (see section 8.7.1 for detailed items): date of sample taken; assessed and signed anonymized lab reports must be sent to sponsor/representatives Inclusion and exclusion criteria validation
- Patient registration in IWRS system
- Patient randomization if all criteria are met.
- Subsequent visits : from visit 1 onwards:
 - Disease evaluation (AML) (see section 8.6)
 - Clinical assessment: vital signs (height, weight, pulse, blood pressure systolic and diastolic), performance status (ECOG score), physical examination findings
 - Study treatment administration (low-dose cytarabine +/- GRASPA): details on date and time of administration are required
 - Patient quality of life: survey EORTC QLQ-C30, transfusion needs, hospitalizations from any cause (except scheduled protocol visit)
 - Biological assessment at D1, D5, D9, D13, D18, D23, D27 (see section 8.7.1 and table 4 for detailed items) instructions to be provided to patient in case of lab testing outside the site hospital; assessed and signed anonymized lab reports must be sent to sponsor/representatives as soon as possible after sampling
 - PK-PD and immunogenicity testing (see section 8.7.2, Table 4 and 5 and Appendix 3 for detailed instructions) only patients on arm B (under GRASPA treatment)
 - IAST (Irregular Antibodies Screening Test) at D9 only patients on arm B (under GRASPA treatment)
 - Review and assessment of any adverse event (refer to section 11 for details)
 - Record of any change in concomitant medications
 - Distribution of patient diary and instructions provided to patients for completion for each visit

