The primary analysis of the main secondary endpoints for efficacy will take place once all patients have completed 12 months in the study as for the primary endpoint. A further supportive set of analyses will take place following completion of 24 months in the study for all patients.

Safety endpoints

All subjects who received at least one dose of investigational products will be included in the safety analyses. Safety data will be summarized using actual treatment received, regardless of randomized treatment.

Safety and tolerability will be assessed in terms of AEs, SAEs, laboratory data and vital signs which will be collected for all subjects. AEs will be coded according to the Medical dictionary for regulatory activities (MedDRA) version 15.1 or higher. The intensity of AEs will be graded according to the NCI-CTCAE (version 4.0).

AEs, AE leading to study treatment discontinuation, AE related to study treatment, and SAEs will be listed individually by subject, and summarized by System Organ Class (SOC) and Preferred Term (PT) by treatment group. Summary of AEs with NCI-CTCAE grade 3 or 4 and most frequent PT will also be provided.

Specific attention will be given to NCI-CTCAE Grade 3 or 4 of pancreatic toxicity, Grade 3 or 4 of hepatotoxicity, allergic reactions or coagulation disorders, known to be potentially related to L-asparaginase as well as to hypoproteinemia and hyperglycemia/diabetes events.

Vital signs and laboratory data will be listed and summarized by actual treatment group based on the safety analysis set. Summary of absolute values over time (one table per vital sign/laboratory parameter) and summary of change from baseline values over time (one table per vital sign/laboratory parameter) will be presented. Patients with vital sign/laboratory values of NCI-CTCAE grade 3 or 4 will be identified.

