3. STUDY DESIGN

3.1. Synopsis of Study Design

This is a multicentre, open label, randomized 1:2 (control versus GRASPA), controlled phase IIb trial in Europe, evaluating efficacy and tolerability of GRASPA. The trial follows the scheme below:

In both treatment and control arms, patients will be treated with subcutaneous LDAC as 40 mg daily (either one single dose of 40 mg or 20 mg twice daily according to local practice) for 10 consecutive days per course, each course occurring every 28 days \pm 3 days, for a duration up to 24 months. Each period of 28 days constitutes a cycle of chemotherapy. The dosage could be adjusted to 20 mg once daily in case of toxicities; a higher dose is also acceptable if required by the patient's status, at the investigator's decision.

In the experimental group, the patients will receive subcutaneous LDAC, as described above, and GRASPA (100 U/kg) given as an intravenous infusion at Day 11 of each 28 day course.

Patients will be required to attend a visit once a month, as the course begins.

When study treatment is stopped (main expected reasons are limiting toxicity, PD, or no evidence of treatment benefit), the visits will take place every 3 months until 24-months study duration has been reached.

An Independent Data Monitoring Committee (IDMC) was set-up for regular data reviews for safety: they reviewed the tolerance of GRASPA when 30 patients had been enrolled, to evaluate limiting toxicities defined as one of the following:

- grade 3 or 4 pancreatic toxicity
- grade 3 or 4 hepatic toxicity, allergic reaction, or coagulation event

- other non-hematologic grade 4 toxicity or requiring treatment change at investigator's decision

Specific attention is paid on type II diabetic patients treated with oral hypoglycemic agents for their diabetes, randomized to LDC + GRASPA.

The IDMC also reviewed safety and tolerance of GRASPA when 60 patients had been enrolled, at the end of recruitment and when 60 PFS events had been observed.

Additional information is provided in the IDMC Charter and the minutes of the IDMC meetings.

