5.2.6. Subpopulations

Analyses (estimated treatment effects and 95% confidence intervals) will be undertaken in relation to OS, PFS and objective response according to the following subgroups and presented in Forest Plots:

- Gender (male/female)
- ECOG PS (0 versus 1 versus 2)
- Age (< 70 / ≥ 70)
- Karyotype (Intermediate risk / High risk)
- Baseline bone marrow blasts, % (< 20% / ≥ 20% to ≤ 30% / > 30%)
- LDH levels at baseline (normal/elevated/unknown)

- FAB (French-American-British) Classification of AML (M1/2 vs. M4/5 vs. M0/6/7)

Other subgroups may be investigated in exploratory analyses.

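### By-visit liver, kidney and pancreas tables combine local-laboratory results without scaling to the local upper limit of normal

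*SAP*

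**What the plan says.** **Where the tests are run.** Protocol section 8.7.1 states: "Biological assessment will be performed according to the investigational center procedure at inclusion", and then on fixed days of every course. Section 8.10, covering visit 1 onwards, foresees "instructions to be provided to patient in case of lab testing outside the site hospital". SAP section 3.1 confirms the setting: "This is a multicentre, open label, randomized 1:2 (control versus GRASPA), controlled phase IIb trial in Europe". In protocol sections 8.7.2 and 8.9 and Appendix 3, central analysis is described only for amino acids, asparaginase, antibodies and bone marrow biomarkers. The text of protocol section 21.2 (Central laboratory) was not available for this check.

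**How results are summarised.** SAP section 5.8.2.1 says: "Raw results as well as absolute and relative change from baseline will be described at each timepoint between treatment groups". It lists the enzymes in U/L and bilirubin in µmol/L. On the formula it says: "Absolute change in the biological parameter between visit V_i and baseline will be calculated according to the formula", followed by a plain subtraction of baseline from the visit value. Relative change divides that difference by baseline. Neither formula contains a reference limit. SAP section 5.2.3 gives no rule for combining data from different sources.

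**Where the plan already works in multiples of the ULN.**
- Protocol section 7.2 sets the creatinine, AST/ALT and bilirubin eligibility limits this way.
- Protocol section 8.5.4 names "bilirubin levels >3 times upper limit of normal or transaminase levels >10 times upper limit of normal", and section 9.5 repeats these limits.
- SAP section 5.2.6 classes baseline LDH as normal, elevated or unknown, which needs a reference limit.

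**Graded and categorised outputs.** SAP section 5.8.2.1 identifies patients with Grade 3 or 4 laboratory values. SAP section 5.8.1 tabulates maximum Grade 1 to 4 for diabetogenic and pancreatic adverse events. SAP section 8.1 lists shift tables from baseline to worst post-baseline result for biochemistry, haematology and coagulation.

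**The concern.** A value in U/L can be compared across patients only if the laboratories share a scale. Here each centre uses its own procedure, and one patient's samples may go to more than one laboratory. The by-arm means, medians and changes may then partly describe which laboratories ran the samples.

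Hepatic and pancreatic toxicity receive specific attention among the safety endpoints. The by-visit tables are where a reader would look for movement in these analytes that did not become a reported, graded event. Noise from mixed scales could hide such movement, and a change of laboratory could produce an apparent rise or fall in a stable patient. Nor can a raw value be placed against the protocol's bilirubin, transaminase and creatinine limits without knowing which laboratory's ULN applies.

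**Working it through.** The plan states no figure on laboratory scaling, so there is none to reproduce. The check is a reading of which planned summary is exposed to what, followed by an illustration of size.

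**1. Which summaries are exposed.** Suppose laboratory 2 reports on a scale c times that of laboratory 1, so that a result at the same multiple of the ULN is c times larger in raw units.
- *Raw value:* differs by the factor c between patients at the same multiple of the ULN.
- *Absolute change, same laboratory throughout:* the same rise in multiples of the ULN also differs by the factor c between patients.
- *Relative change, same laboratory throughout:* (cV - cB)/(cB) = (V - B)/B, where V is the visit value and B the baseline value. The factor c cancels.
- *Patient who changes laboratory:* c does not cancel in any of the three. With no true change, relative change is c - 1 when moving to the higher scale and 1/c - 1 when moving to the lower.

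**2. Size for a patient who switches, and for reading a raw value.** The documents give no local ULNs, so c = 1.25 to 3 is an assumption. It is also assumed that the ratio of the ULNs reflects the ratio of the assay scales.

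| c | Switch up, no true change (c - 1) | Switch down (1/c - 1) | Raw value at 3 x ULN in laboratory 1, read in laboratory 2 (3/c) | Same at 10 x ULN (10/c) |
|---|---|---|---|---|
| 1.25 | +25% | -20% | 2.4 x ULN | 8.0 x ULN |
| 1.5 | +50% | -33% | 2.0 x ULN | 6.7 x ULN |
| 2 | +100% | -50% | 1.5 x ULN | 5.0 x ULN |
| 3 | +200% | -67% | 1.0 x ULN | 3.3 x ULN |

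In multiples of the ULN, the same switch with no true change gives 0.

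**3. Size of a chance difference between arms in raw values.** Randomisation is stratified by performance status only (SAP section 3.2), so laboratory mix is balanced between arms only by chance. Take 82 and 41 patients (SAP section 5.1) and assume two laboratories, each serving half the patients.
- SE of the difference in laboratory share = sqrt[0.25 x (1/82 + 1/41)] = 0.0956, so the 95% limit is 1.96 x 0.0956 = 0.187.
- Shift in the mean raw value at that limit, with identical multiples of the ULN in both arms = 0.187 x (c - 1) / [1 + 0.5(c - 1)].
- Results: 4.2% (c = 1.25), 7.5% (c = 1.5), 12.5% (c = 2), 18.7% (c = 3).

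These are values at the 95% limit of chance, not expected differences.

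**4. What the other outputs cover.**
- The Grade 3 or 4 identification and the graded adverse event tables do not depend on pooled means, but they leave those means unchanged.
- The Grade 1 to 4 table includes asymptomatic, biochemical pancreatitis. SAP section 5.8.1 specifies no equivalent breakdown for liver events.
- Protocol section 11.1.2.1 lets an investigator leave an abnormal value unreported as an adverse event if it is a scheduled test, has no symptoms, is judged not medically significant and leads to no change in treatment. Some lower-grade enzyme changes could therefore appear only in the laboratory outputs.
- The SAP text does not define the scale or categories of the shift tables.
- The laboratory listings are headed as SI units. That aligns units, but not assays or reference limits.

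**The case against.** The case against is substantial, and much of it stands.

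- **Relative change is planned.** It removes a proportional laboratory difference while the patient stays in one place. A reader might infer that every planned summary is distorted between patients. The formulas do not support that.
- **Grading reaches below Grade 3.** A reader might infer that grades serve only to flag Grade 3 or 4 patients. The pancreatic adverse event table in SAP section 5.8.1 shows otherwise. The named endpoints are themselves defined by grade.
- **The shift tables may already be suitable.** SAP section 1 puts output specifications in a separate document, which may define them.
- **The protocol's limits are only partly on the ULN scale.** A reader might infer that all liver and pancreas limits are. Protocol section 8.11 uses grades for hepatic toxicity, and the pancreatic rules in sections 8.11 and 9.5 also use grades. No ULN-based limit for lipase or amylase is given. Nor would a mean in multiples of the ULN show which patients crossed an individual limit, so counts are needed as well.
- **A loss of precision is tempting to quote.** Suppose ULNs spread evenly on the log scale over a k-fold range and the within-laboratory SD of log values is s. Variance then rises by the factor 1 + [ln(k)/sqrt(12)]²/s². This is 1.11 for k = 2, s = 0.6, and 2.00 for k = 4, s = 0.4, but only about 1.01 for k = 1.25, s = 0.6. A reader might turn the larger figures into patients lost. The tables are descriptive, the SAP plans no log transformation, and the formula does not apply to relative change within one laboratory, so that translation is not warranted.
- **Bias between arms is not shown.** The GRASPA arm has extra procedures on days 9 and 11 and extra samples later in the course. A reader might infer that the control arm uses outside laboratories more often. The documents do not say so. Only chance imbalance can be assumed.

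None of this puts the raw values and absolute changes on a common scale, or protects relative change when a patient changes laboratory.

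**Conclusion.** The point holds as a limited one. As written, SAP section 5.8.2.1 mixes laboratory scales between patients in raw values and absolute changes, and within any patient who changes laboratory in all three summaries. What follows is noise, and possible spurious within-patient change, in descriptive safety tables. The graded outputs and shift tables soften this without removing it.

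The size cannot be established. The number of laboratories, the spread of their ULNs and the frequency of switching are not given. The range of +25% to +200%, or -20% to -67%, for a steady patient who switches rests entirely on the assumed 1.25- to 3-fold ratio of ULNs. If the ULNs are close and switching is rare, the effect is small. The conclusion also assumes that safety chemistry is not analysed centrally, which agrees with protocol section 8.7.1.

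This is an improvement that would be nice to have. It does not affect the overall survival analysis, the sample size or the adverse event grades.

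**What to change.** Amend SAP section 5.8.2.1 and the output specifications as follows.

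1. For AST, ALT, GGT, alkaline phosphatase, LDH, bilirubin, creatinine, lipase and amylase, add by-arm summaries of value, change from baseline and worst post-baseline value as multiples of the ULN of the laboratory that ran the sample. State how many results lack a ULN.
2. Keep raw values in the listings.
3. Define the biochemistry shift tables by CTCAE grade or by category of multiple of the ULN.
4. Add by-arm counts of patients exceeding the limits already in protocol sections 8.5.4 and 9.5 (bilirubin >3 x ULN, transaminases >10 x ULN). This is a reporting count only. It takes no view on those limits or on how they relate to the grade-based rules in section 8.11.

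The cost is SAP wording, one derivation and recording the local ULN with each result. Local limits are already needed for eligibility, for the liver limits and for the LDH subgroup, and protocol section 8.7.1 already has laboratory reports sent to the sponsor. The documents do not say whether the eCRF stores the ULN, so this should be checked first. If a laboratory identifier is also held, reporting how many patients changed laboratory would show how much the point matters.

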5.8.2.2. Amino-acids and total blood asparaginase

This procedure is applicable to patients under GRASPA® treatment only.

Amino acids will be described at D11 and D18 of the first two cycles of chemotherapy on all patients, at D11 and D18 of every remaining cycle for patients included before the protocol amendment and at D13 and D27 of the first two cycles for patients included after the protocol amendment:

- asparagine
- aspartate
- glutamine
- glutamate

Total blood asparaginase will be described at D11 and D18 of the first two cycles of chemotherapy on all patients, at D11 and D18 of every remaining cycle for patients included before the protocol amendment and at D13 and D27 of the first two cycles for patients included after the protocol amendment:

- Plasmatic asparaginase
- Total asparaginase
- Encapsulated asparaginase
- Free asparaginase

Encapsulated asparaginase is defined as: $\text{Total asparaginase} - \text{Plasmatic asparaginase}$.

Free asparaginase is defined as: $\text{Plasmatic asparaginase} / \text{Total asparaginase}$

For lab values reported in the format BLLQ (Below Lower Limit of Quantification), the value of limitation should be used for the purpose of including this data in the calculation of summary statistics:

Parameters	Lower limit of quantification
Asparagine	0.519 µmol/L*
Aspartate	0.987 µmol/L*
Glutamine	49.802 µmol/L*
Glutamate	10.716 µmol/L*
Plasmatic asparaginase	2.5 U/L*
Total asparaginase	75 U/L *

* These data will depend of the central laboratory, and will be confirmed before analyses.

Raw results as well as absolute and relative change from D11 will be described at each time point between treatment groups, and presented separately for patients recruited before and after the protocol amendment.

Absolute change in biological parameter between D18 and D11 will be calculated according to the formula: *Biological parameter at D18 – Biological parameter at D11*

Relative change in biological parameter between D18 and D11 will be calculated according to the formula:

$$\frac{\text{Biological parameter at D18} - \text{Biological parameter at D11}}{\text{Biological parameter at D11}} \times 100$$

5.8.3. Vital Signs and Physical Examinations

Raw results as well as absolute and relative change from baseline for weight, ECG, heart rate, systolic and diastolic blood pressure will be described at each visit between treatment groups.

Absolute change in vital signs between visit V_i and baseline will be calculated according to the formula: *Vital signs at V_i – Vital signs at baseline*

Relative change in vital signs between visit V_i and baseline will be calculated according to the formula:

$$\frac{\text{Vital signs at } V_i - \text{Vital signs at baseline}}{\text{Vital signs at baseline}} \times 100$$

By-subject listings of vital sign measurements will be presented in data listings and patients with vital sign values of NCI-CTCAE grade 3 or 4 will be identified.

